3.1.3 Phase 2: 3-month visit

Participants randomized to both groups will receive monthly phone calls and come back at 3 months for a visit. Sleep study and all procedures performed at the baseline visit, except for physical examination, will be repeated at 3 months. Medication canisters will be weighed. Participants in the placebo group will then be referred to clinical care (for evaluation for further clinical treatment such as surgery if their sleep study is still abnormal, or for routine ongoing clinical surveillance if their sleep study has normalized). Children in the NCS group will be referred to clinical care if their sleep study shows severe OSAS or significant hypoxemia or hypercapnia, such that definitive treatment should not be delayed (AHI $> 30/\text{hr}$, more than 2% total sleep time with SpO₂ $<90\%$, end-tidal PCO₂ $> 60 \text{ mm Hg}$ for > 5 minutes, or pathologic arrhythmias)(4). In addition, children with (i) DXA scans showing spine or whole body bone mineral density < -2.0 standard deviations using race specific curves with adjustment for height Z-score, (ii) ophthalmologic exam showing cataracts or intra-ocular pressure $> 22 \text{ mm Hg}$ on two measurements will be withdrawn from the study and referred to clinical care. Note that DXA results may not be available on the same day, in which case the participant will be randomized, but will later be withdrawn from the study and referred for clinical care if the DXA results are abnormal.

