3.2 Allocation to Treatment Groups and Blinding

Randomization: A blocked randomization scheme (with block sizes that vary randomly between 2 and 4) will be employed to initially randomize subjects to NCS or placebo at baseline; the same approach will then be employed for the re-randomization at 3 months, when the subjects who were initially randomized to receive NCS will be re-randomized in equal numbers to receive NCS or placebo. The randomization will be stratified according to atopy/asthma, current use of inhaled corticosteroids for asthma (yes/no), obesity status and seasonality (spring/summer vs autumn/winter). Programs will be written in Stata to conduct the randomization, and the assignments will be stored in sealed envelopes stored in a locked cabinet that is only accessible to CTSA staff who are not affiliated with other aspects of the

study.

Blinding: The study will be double-blinded. All subjects, their families, investigators and study team members will be blinded, except for one research coordinator. In order to avoid bias and equipoise shifting, two research coordinators will be part of this study. One of them will be responsible for enrolling subjects and will be blinded to the treatment allocation status. The other research coordinator will be responsible for breaking the blind at the 3 month visit. She will refer participants allocated to placebo to clinical care, and communicate with the statistician regarding the randomization of participants initially allocated to NCS. Other investigators will evaluate research data (e.g., read polysomnograms) that are deidentified and coded to prevent becoming unblinded. Note that there is no physical exam after the baseline study. The statistician will generate a list of random numbers for study arm assignment, and a CTSA staff member who is not otherwise involved in the study will provide the drug/placebo.

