4.3 Phase 2 of the Study

Participants randomized to both groups will receive monthly phone calls, keep an infection log, and come back at 3 months for a visit.

4.3.1 Visit 2

Detailed description of study visit including all procedures – listed like above examples.

- Sleep study
- Vital Signs
- Cognitive and behavioral measures
- Knee height measurement,
- DXA scan (immediately preceded by pregnancy test when indicated)
- Phlebotomy (biomarkers, genetics, and cortisol levels)
- Nasal swab (biomarkers, genetics)
- Ophthalmology evaluation
- OSAS symptoms questionnaires
- Nasal symptoms questionnaires
- Quality of life questionnaires
- Airway size measurement
- Weigh medication canister
- Participants in placebo group will end their participation in the study at the end of visit 2. They will be referred to clinical care
- Re-randomization of participants in NCS group
- Dispensation of NCS or placebo

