8.8 Treatment Assignment Methods

8.8.1 Randomization

A blocked randomization scheme (with block sizes that vary randomly between 2 and 4) will be employed to initially randomize subjects to NCS or placebo at baseline; the same approach will then be employed for the re-randomization at 3 months, when the subjects

who were initially randomized to receive NCS will be re-randomized in equal numbers to receive NCS or placebo. An exception for this randomization schedule will be siblings. Specifically, siblings will be randomized to the same arm to avoid parental confusion with study drug administration. For example, parents may confuse study drug with placebo because both study drug and placebo look, taste and smell identical and parents may give the wrong medication to their children. The randomization will be stratified according to atopy/asthma, current use of inhaled corticosteroids for asthma (yes/no), obesity status and seasonality (spring/summer *vs* autumn/winter). Programs will be written in Stata to conduct the randomization, and the assignments will be stored in sealed envelopes stored in a locked cabinet that is only accessible to CTSA staff who are not affiliated with other aspects of the study.

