8.8.2 Blinding

The study will be double-blinded. All subjects, their families, investigators and study team members will be blinded, except for one research coordinator as previously described. The statistician will generate a list of random numbers for study arm assignment, and a CTSA staff member who is not otherwise involved in the study will provide the drug/placebo.

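### The same-arm rule for siblings has no time limit, so a sibling enrolled after the first child's 3-month visit could have a first arm that the family can infer

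*Combined protocol and SAP*

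**What the plan says.** All references are to the combined protocol and SAP.

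- **Sibling rule (8.8.1).** Siblings are an exception to the blocked, stratified schedule: "siblings will be randomized to the same arm to avoid parental confusion with study drug administration". The reason given is that drug and placebo cannot be told apart, so "parents may give the wrong medication to their children". The rule sets no time limit and does not separate siblings enrolled together from those enrolled later. Section 3.2, which otherwise gives the same randomization scheme, omits the exception.
- **Month 3, placebo children (4.3.1).** "Participants in placebo group will end their participation in the study at the end of visit 2".
- **Month 3, NCS children (8.8.1, 3.1.3).** Re-randomization is for the children "who were initially randomized to receive NCS will be re-randomized in equal numbers to receive NCS or placebo". Some do not reach it: "Children in the NCS group will be referred to clinical care if their sleep study shows severe OSAS or significant hypoxemia or hypercapnia". Abnormal DXA or eye findings also lead to withdrawal.
- **Code break (3.2).** Two coordinators are used to limit bias. One enrols and stays blinded. "The other research coordinator will be responsible for breaking the blind at the 3 month visit".
- **Blinding (8.8.2).** "All subjects, their families, investigators and study team members will be blinded, except for one research coordinator as previously described".
- **Duration (synopsis).** Participation lasts 3 months for children first given placebo and 12 months for those first given NCS. The whole study is expected to last 5 years.

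**The concern.** Whether a child stays in the study after Visit 2 carries information about that child's first arm. For a single child this does no harm to the 3-month comparison, because the primary data are already collected. The sibling rule carries the information forward to a child who has not yet been randomized. Read literally, a brother or sister enrolled after that visit takes the first child's arm, and that arm may by then be known or nearly known.

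Concealment and blinding are both at stake for such a child. Parents could agree when they expect NCS and decline when they expect placebo, so that entry depends on arm. Caregivers give the spray (7.1.3, 7.2.3), so use could depend on it too. Questionnaires and the infection log that families complete could be filled in with the arm in mind. This is a separate matter from correlation between siblings' outcomes.

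**Working it through.** **1. The plan's own figure.** Section 6.4 states 81% power at effect size 0.50 with 100 NCS and 50 placebo children, two-sided 0.05. Noncentrality = 0.50 / √(1/100 + 1/50) = 0.50 / 0.1732 = 2.89 on 148 degrees of freedom, which gives power 81.8%. The group sizes follow from 5% dropout: 106 × 0.95 = 100.7 and 53 × 0.95 = 50.4. The stated figure is reproduced, but it does not decide this point, which turns on the text.

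**2. The rules side by side, for a sibling enrolled after the first child's Visit 2.**
- 8.8.1: the sibling takes the first child's arm.
- 4.3.1 and 8.8.1: a first child on placebo has left; only a first child on NCS can have continued.
- 3.2 and 8.8.2: families, investigators and staff, except one coordinator, do not know the arm.

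No section bars, delays or separately randomizes this sibling. If the family knows the rule, the three statements cannot all hold.

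**3. How much is disclosed.** Before any information, the probability of placebo is 53/159 = 0.33.
- *First child continued.* Only NCS children continue, so the probability that the initial arm was NCS is 1.
- *First child left.* Let x be the share of NCS children who also leave at month 3. The documents do not give it, so 0 to 10% is an assumption. With 50 placebo and 100 NCS children at that visit, P(placebo | left) = 50 / (50 + 100x).

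| x (assumed) | P(placebo given exit) |
|---|---|
| 0 | 50/50 = 1.00 |
| 2% | 50/52 = 0.96 |
| 5% | 50/55 = 0.91 |
| 10% | 50/60 = 0.83 |

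**4. Possible effect on the primary comparison.** No sibling count is given. Assume that later siblings are 2% to 10% of the 150 analysed (3 to 15 children), and that knowing the arm shifts the between-arm contrast among them by 0.25 to 0.5 SD. Overall bias = share × shift: from 0.02 × 0.25 = 0.005 SD to 0.10 × 0.5 = 0.05 SD. With no true effect, the rejection rate of the 100 versus 50 t-test would be 5.0% to 5.9% instead of 5%.

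**5. Power if later siblings were left out of the primary analysis (effect size 0.50).**

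| Share left out (assumed) | NCS vs placebo | Power |
|---|---|---|
| 2% | 98 vs 49 | 81.0% |
| 5% | 95 vs 48 | 80.1% |
| 10% | 90 vs 45 | 77.6% |

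**The case against.** The best defence is that the rule's own reason presupposes two children on study drug at once. A sensible coordinator would not apply it after the first child has left, so this may be loose wording with no intention to assign a known arm. That is fair as to intent. It does not remove the problem, because the rule as written covers later siblings and nothing else in the protocol excludes them.

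Four stronger readings are tempting, and the documents do not support them.

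- **That disclosure is complete.** Exit at month 3 does not prove placebo, since section 3.1.3 also sends some NCS children out and section 4.8 allows withdrawal at the investigator's discretion.
- **That the sibling of a continuing child is bound to get NCS.** This holds only if the shared arm means the initial arm. Half of the continuing children are switched to placebo at month 3, still blinded. If the rule means matching the first child's current bottle, the sibling's treatment is not disclosed. The protocol does not say which is meant.
- **That parents and the consenting investigator know the sibling's arm before consent.** No section says that families are told the rule. Section 3.2 keeps the enrolling coordinator blinded, and section 8.13 says only that an investigator obtains consent. What can be said is that a family aware of the rule, or staff who see whether the first child continued, could work it out.
- **That the primary result is compromised, or that most siblings enrolled separately would be affected.** AHI comes from sleep studies read from coded records (3.2), and adherence is checked by canister weight (7.1.4). The symptom, behaviour and quality-of-life questionnaires are not among the secondary endpoints in section 6.2; the infection log is the clearest parent-reported item there. A 5-year study makes late siblings possible but says nothing about how many there will be.

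**Conclusion.** The point holds in a limited form. The unlimited same-arm rule, taken with the month-3 exit of every placebo child, can give a later-enrolled sibling an inferable first arm. Under the initial-arm reading, the inference is certain when the first child continued. When the first child left, it has probability 0.83 to 1.00 under the assumed NCS exit rate of 0 to 10%. That conflicts with the blinding in sections 3.2 and 8.8.2, and it opens entry, adherence and parent-reported data to influence by arm.

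The number of children is unknown and may be zero. The bias of 0.005 to 0.05 SD rests wholly on assumed shares and shifts, and it suggests a small effect on AHI. This is a minor point, worth correcting because the rule does nothing for its stated purpose once the first child is off study drug.

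**What to change.** In sections 3.2 and 8.8.1:

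1. Limit the same-arm rule to siblings randomized at the same time, within the same baseline period. A cut-off at the first child's Visit 2 is not enough: a sibling randomized one month before that visit would have an inferable arm for the last two of three treatment months.
2. State that a sibling who presents later is randomized independently by the normal schedule once no sibling is on study drug, and is not enrolled until then. This restores concealment and also removes the bottle mix-up, so late siblings need not be refused outright.
3. Define what the same arm means for siblings at the month-3 re-randomization.
4. Add the sibling exception to section 3.2 so that the two randomization texts agree.
5. Report the number of sibling sets.

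The cost is a few sentences. The planned sample size does not change. The downside is that a few siblings are delayed or lost: the wait runs until the first child finishes, at most 3 months from that child's randomization if first given placebo and 12 months if first given NCS.

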8.8.2 Blinding

The study will be double-blinded. All subjects, their families, investigators and study team members will be blinded, except for one research coordinator as previously described. The statistician will generate a list of random numbers for study arm assignment, and a CTSA staff member who is not otherwise involved in the study will provide the drug/placebo.

8.8.3 Unblinding

An unblinded medical monitor (*[name] at Johns Hopkins University) will review any adverse events but the investigators will remain blinded.

8.9 Data Collection and Management

1. Confidentiality.
 - Data will be uploaded directly and stored in a password-protected file using the Research Electronic Data Capture (REDCap).
2. Security. A copy of the password-protected file will be stored on the PI's office computer, with the original in research secure server.
3. Anonymization. The identifiers will be destroyed after publication. The other data will be retained indefinitely.

8.10 Confidentiality

All data and records generated during this study will be kept confidential in accordance with Institutional policies and HIPAA on subject privacy and the Investigator and other site personnel will not use such data and records for any purpose other than conducting the study.

No identifiable data will be used for future study without first obtaining IRB approval. The investigator will obtain a data use agreement between the provider (the PI) of the data and any recipient researchers (including others at CHOP) before sharing a limited dataset (PHI limited to dates and zip codes).

8.11 Regulatory and Ethical Considerations

8.11.1 Data and Safety Monitoring Plan

- The study will have an external Data Safety Monitoring Board (DSMB) and an external unblinded medical monitor.
- The role of the medical monitor will be similar to that used in the Childhood Adenotonsillectomy Trial (CHAT) trial.(4) The Medical Monitor ([name], Johns Hopkins University) is a pediatric pulmonologist and sleep specialist. She will have access to unblinded data should the need arise for a “real time,” clinically urgent decision regarding a subject’s continued study participation. A class of outcomes will be established denoted as “Treatment Failures.” This will be defined as a change in clinical status interpreted by the safety officer as requiring an immediate change to established clinical therapy for OSAS. Operationally, treatment failures will be identified by the research coordinator based on interim telephone calls and research visits, or contacts initiated by the subject. Information will be submitted to the safety officer who will make a final adjudication of the status of the subject. Data will be subsequently reviewed by the DSMB. The P.I. will make the final determination regarding withdrawing individual subjects. Note that as the study will utilize an intent to treat paradigm, every effort will be made to continue the subject in the study, regardless of whether the subject receives clinical treatment or not. Examples of treatment failures include worsening symptoms of OSAS such as sleepiness interfering with schoolwork, or development of complications associated with OSAS such as failure to thrive. Note that in the CHAT study there were only 9 of 464 (1.9%) children designated as treatment failures, so the numbers in the current study are expected to be low.
- The DSMB will be responsible for overall participants’ safety during the study. The DSMB will be comprised of a pediatric pulmonologist, [name] [name]; a neonatologist and sleep medicine expert, [name]; a pediatric otolaryngologist, [name]; and a biostatistician, [name].
- DSMB members are experts in their field and are unrelated to this research.
- DSMB members do not have active or pending scientific collaborations with study investigators
- The DSMB will meet twice a year. The meetings will be held via teleconference.
- Once a month, the Medical Monitor and DSMB will receive reports of all adverse events
- On a quarterly basis, or more frequently if needed, summary reports of all AEs, SAEs, Urgent/Immediate Medical Referrals, and Treatment Failures by treatment arm also will be provided to the DSMB

- For each DSMB meeting, reports will be provided. These will include data on recruitment and baseline characteristics, pooled data on eligibility violations, completeness of follow-up and compliance, analyses of primary and secondary efficacy endpoints, subgroup and adjusted analyses, analyses of AEs and symptom severity, and analyses of laboratory data. The study statistician will prepare these reports.
- The reports will provide information that is accurate, with follow-up that is complete to within one month of the date of the DSMB meeting. The Reports will be provided to DSMB members approximately one week prior to the date of the meeting.
- Minutes for each meeting will be prepared

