Study Design	
 • Randomized, parallel, double-blind, placebo-controlled study.
Subject Population key criteria for Inclusion and Exclusion:	
Inclusion Criteria
 
 1. Subjects age 5-12 years. 2. Mild to moderate OSAS, defined as an obstructive apnea index (AI) of 1-20/hr of total sleep time (TST) or AHI 2-30/hr of TST. 3. Parent-related symptoms of habitual snoring (>3 nights per week). 4. No history of adenotonsillectomy or prior NCS use. 
Exclusion Criteria
 
 1. Severe OSAS or significant hypoxemia or hypercapnia on polysomnography (PSG), such that definitive treatment should not be delayed (AHI > 30/hr, more than 2% total sleep time with SpO₂ <90%, end-tidal PCO₂ > 60 mm Hg for \geq 5 minutes, pathologic arrhythmias). 2. History of recurrent throat infections 3. Any NCS use in the past 3 months, or NCS use for \geq 2 weeks in the past year 4. Abnormalities on baseline safety screening tests 5. Previous adenotonsillectomy 6. Previous adenoidectomy unless adenoidal tissue has been documented to have regrown 7. CPAP therapy 8. Pregnancy
Number Of Subjects	
 • 318 children will be recruited at CHOP. This is a single center study

Study Duration	
 • The participation of subjects randomized to the placebo group at the baseline visit will be 3 months. • The participation of subjects randomized to the NCS group at the baseline visit will be 12 months. • The entire study is expected to last 5 years
Study Phases	(1) Screening : screening for eligibility and obtaining consent and
Screening	(2) Intervention : Randomization: placebo or NCS for 3 months
Study Treatment	(3) Follow-up : randomization of NCS group to placebo or
Follow-Up	continuation of NCS for 9 months
Efficacy Evaluations	Change in AHI in the placebo and NCS groups at 3 months of therapy; and at 12 months of therapy
Pharmacokinetic Evaluations	N/A
Safety Evaluations	Worsening symptoms of OSAS, such as daytime sleepiness or development of complications, such as failure to thrive,

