6.5 Interim Analysis

There will not be an interim analysis as this study does not involve a life-threatening condition or a life-threatening outcome.

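### Do the efficacy analyses in the twice-yearly DSMB reports contradict the statement that there is no interim analysis?

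*Combined protocol and SAP*

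**What the plan says.** Section 6.5 is a single sentence: "There will not be an interim analysis as this study does not involve a life-threatening condition or a life-threatening outcome". Section 8.11.1 sets out the monitoring: "The DSMB will be responsible for overall participants’ safety during the study", and "The DSMB will meet twice a year". The report for each meeting is to contain, among other items, "pooled data on eligibility violations, completeness of follow-up and compliance" and then "analyses of primary and secondary efficacy endpoints, subgroup and adjusted analyses, analyses of AEs and symptom severity". On authorship it says "The study statistician will prepare these reports". The separate quarterly safety summaries are explicitly split by arm: "Treatment Failures by treatment arm also will be provided to the DSMB". The synopsis gives the length: "The entire study is expected to last 5 years".

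Sections 3.2 and 8.8.2 describe a double-blind trial in which one research coordinator is the only unblinded member of the study team. Both sections have the statistician produce the random list for arm assignment. Section 3.2 adds that the unblinded coordinator contacts the statistician about re-randomizing the children whose first allocation was NCS.

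**The concern.** An analysis of the primary endpoint while the trial is running is, in ordinary usage, an interim analysis. A reader who sets 6.5 beside 8.11.1 finds one section denying it and another scheduling it for every board meeting, with no stated purpose, no stopping guideline and no alpha adjustment. If such looks could end or reshape the trial, the nominal 5% error rate would not hold.

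The blinding text raises a second question. Only children first given NCS are re-randomized, so the coordinator's contact tells the statistician their first-phase arm. If the same person prepares by-arm AHI tables for the board, that person could see the treatment comparison while the synopsis still leaves the primary test open between a t-test and a Wilcoxon test. A final report could then state that there was no interim analysis and that only one team member was unblinded, although 8.11.1 had been followed to the letter.

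**Working it through.** **1. The plan's own figure.** Inputs from section 6.4: effect size 0.50, 100 NCS and 50 placebo children analysed, two-sided 0.05, one final t-test.

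- Noncentrality = 0.50 / √(1/100 + 1/50) = 0.50 / 0.1732 = 2.887.
- The critical t on 148 df is 1.976, and the noncentral t gives power of 81.8%.
- The normal approximation gives Φ(2.887 − 1.960) = Φ(0.927) = 82.3%.

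The plan states 81%, so the figure reproduces. It assumes a single final test, as 6.5 implies.

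**2. How many reports.** 2 meetings per year × 5 years = at most about 10. Fewer will carry usable primary data, because no child has a 3-month AHI until three months after randomization. The plan does not give the number.

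**3. What the looks could do to type I error.** The question is whether a look can change the trial.

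- If no look is acted on, there is one final test and the error rate is 5%.
- For scale only, suppose every look were tested at an unadjusted two-sided 0.05 and acted on. One million simulated null trials per case, with equally spaced looks (an assumption), give:

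| Looks | Overall type I error |
|---|---|
| 2 | 8.3% |
| 5 | 14.2% |
| 8 | 17.6% |
| 10 | 19.4% |

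The table needs a rule for stopping or changing the trial for benefit. Section 8.11.1 gives the board responsibility for safety, and the data and safety monitoring paragraph after the synopsis names adverse events and treatment failures as what is monitored. No section gives the board authority over efficacy. The reason offered in 6.5, that neither condition nor outcome is life-threatening, is a reason for not planning early stopping. The table therefore does not describe this plan.

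**4. Why a safety board would receive these endpoints.** Section 5.4 lists sleep study results among the safety measures, and the AHI comes from the sleep study. Section 3.1.3 uses an AHI threshold at 3 months to refer children in the NCS group to clinical care. Section 6.3.2, under its efficacy heading, names knee height, bone health, adrenal suppression, ocular health and infection as secondary endpoints. In this trial the primary and secondary efficacy endpoints are therefore largely the safety data as well. Only the subgroup and adjusted analyses lack an evident safety use.

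**5. Whether the DSMB reports worsen the open choice of test.** Null trials of 100 vs 50 were simulated under four assumed distributions of AHI change: normal; t with 3 df; and two skewed cases, with lognormal baseline (median 5, log-SD 0.7) and multiplicative lognormal noise of log-SD 0.5 or 0.7. There were 100,000 trials per distribution, or 20,000 for the normality-check row.

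| How the test is chosen | Type I error across the four cases |
|---|---|
| t-test fixed | 4.5–4.9% |
| Wilcoxon fixed | 4.9% |
| Chosen by a normality check on residuals | 4.9–5.2% |
| Smaller p at 50 vs 25, applied to the full data | 5.5–6.5% |
| Smaller p at 80 vs 40, applied to the full data | 5.8–7.2% |
| Smaller p on the final data | 5.9–7.5% |

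A separate run of 20,000 trials per case, without the normality-check row, agreed within simulation error. The ordinary ways of settling the choice stay close to 5%. The last three rows need someone to pick the test by its result, which nothing in the documents suggests. Even then, a DSMB report gives less inflation than the final data would. The open choice exists with or without a DSMB, and the reports do not enlarge it.

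**The case for a change.** The strongest contrary case is that the text itself is inconsistent, whatever the error rate. Section 6.5 does not say that it means only the absence of a formal stopping look, and 8.11.1 does not say why subgroup and adjusted analyses go to a safety board. The omission of the statistician from the list of unblinded people needs no inference about the DSMB tables, since the re-randomization contact alone discloses first-phase arm. Clarifying all this would cost only a few words.

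Much of that is fair as a comment on drafting. The single-coordinator statement is incomplete, and the purpose and format of the efficacy tables are unstated. But the weightier consequence, one analyst watching AHI by arm and then choosing the test, rests on two inferences. The first is that the tables are by arm; how far the word pooled reaches along the list of report contents is unclear. The second is that one statistician does everything. The plan names no other person for these tasks, but title and signature pages are not available, so silence about staff is weak evidence. The statistician's tasks are also set out in the same section as the blinding statement, so a reader is not misled. Outcome measurement has its own protection: 3.2 has polysomnograms read from de-identified, coded records and keeps assignments in sealed envelopes open only to CTSA staff. Taking AHI comparisons out of the DSMB reports would be a trade-off rather than a repair, since it would narrow the board's view of benefit against risk.

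**Conclusion.** The concern does not call for a change. Sections 6.5 and 8.11.1 can be read together: efficacy endpoints go to a safety board as context, most of them are safety measures too, and no look can stop or alter the trial for benefit. On that reading the type I error is 5% with a test fixed in advance (4.9–5.2% in simulation if a normality check picks it), and power at an effect size of 0.50 is 81.8% against the stated 81%. Sample size and outcome scoring are untouched.

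What is left is a clerical slip in the blinding statement, which omits the statistician, and a gap about the purpose and format of the DSMB tables that the board and the statistician would fill sensibly in practice. The choice between t-test and Wilcoxon is a separate matter on which statisticians differ, and it does not depend on the DSMB reports.

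The conclusion assumes that the board keeps to its stated safety role and that the primary test is not chosen by its result. The documents give no reason to doubt either. A documented power to stop for efficacy would change the conclusion, and there is none.
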